10.4.3 Instructions for reporting serious adverse events

In the case of occurrence of an SAE, the Investigator or any designees must immediately:

- ENTER (within 24 hours) the information related to the SAE in the appropriate screens of the e-CRF; the system will automatically send a notification to the monitoring team after approval of the Investigator within the e-CRF or after a standard delay.
- SEND (preferably by fax or e-mail) a photocopy of all examinations carried out and the dates on which these examinations were performed, to the representative of the monitoring team whose name, fax number, and email address appear on the clinical trial protocol. Care should be taken to ensure that the patient's identity is protected and the patient's

identifiers in the clinical trial are properly mentioned on any copy of a source document provided to the Sponsor. For laboratory results, include the laboratory normal ranges.

- All further data updates should be recorded in the e-CRF as appropriate, and further documentation as well as additional information (for laboratory data, concomitant medications, patient status, etc) should be sent (by fax or e-mail) to the monitoring team within 24 hours of knowledge of the SAE. In addition, every effort should be made to further document any SAE that is fatal or life-threatening within a week (7 days) of the initial notification.
- A back-up plan (using a paper case report form [CRF] process) is available and should be used when the e-CRF system does not work.

Any SAE brought to the attention of the investigator at any time after the end of the study for the patient and considered by him/her to be caused by the IMP with a reasonable possibility, should be reported to the monitoring team.

10.4.4 Guidelines for reporting adverse events of special interest

For AESIs, the Sponsor must be informed immediately (ie, within 24 hours), as per SAE notification guidelines described in [Section 10.4.3](#), even if not fulfilling a seriousness criterion, using the corresponding pages of the CRF (to be sent) or screens in the e-CRF.

For reporting unusual lack of efficacy for Canadian patients:

To be in line with Canadian Regulations, any AE that can be related to an unusual lack of efficacy (definition in [Section 10.4.1.3](#)) in the Investigator's judgment must be reported to the Sponsor in an expedited report even if a seriousness criterion hasn't been met. Consequently, as soon as the Investigator is informed by the patient of the occurrence of an AE that can be related to unusual lack of efficacy, he/she must immediately report this event on the AE page of the e-CRF. Even if the seriousness criterion has not been met, a paper copy of the SAE Complementary form and the Follow-up Information form (if needed) must still be completed:

- ENTER (within 1 working day) the information related to the unusual lack of efficacy in the appropriate screens of the e-CRF (AE screen);
- SEND (by fax) a printed copy of the AE form and a paper copy of the completed SAE Complimentary form to the representative of the Monitoring Team whose fax number appear on the Clinical Trial Protocol. Send also any photocopy of all examinations carried out and the dates on which these examinations were performed. Care should be taken to ensure that the patient's identity is protected and the patient's identifiers in the Clinical Trial are properly mentioned on any copy of source document provided to the Sponsor. For laboratory results, include the laboratory normal ranges.

Instructions for AE reporting are summarized in [Table 6](#).

Table 6 - Summary of adverse event reporting instructions

Event category	Reporting timeframe	Specific events in this category	Case Report Form completion		
			AE form	Safety Complementary Form	Other specific forms
Adverse Event (non-SAE, non-AESI)	Routine	Any AE that is not SAE or AESI	Yes	No	No
Serious Adverse Event (non-AESI or AESI)	Expedited (within 24 hours)	Any AE meeting seriousness criterion per Section 10.4.1.2	Yes	Yes	No
Adverse Event of Special Interest	Expedited (within 24 hours)	Pregnancy	No	No	Yes
		Symptomatic overdose	Yes	No	Yes
Adverse Event of Special Interest (Canada only)		Unusual lack of efficacy of IMP, Canada only	Yes	Yes	No

10.5 OBLIGATIONS OF THE SPONSOR

During the course of the study, the Sponsor will report in an expedited manner:

- All SAEs that are both unexpected and at least reasonably related to the IMP (suspected unexpected serious adverse reaction [SUSAR]), to the regulatory authorities, independent ethics committees (IECs)/institutional review boards (IRBs) as appropriate and to the Investigators.
- All SAEs that are expected and at least reasonably related to the IMPs to the regulatory authorities, according to local regulations.
- For Canada, Phase IV studies will follow post-marketing regulatory requirements. Reports of unusual lack of efficacy (serious or not), originating from Canada, will be submitted to the Canadian regulatory authority, according to local regulations.

In this study, some AEs are considered related to the underlying condition and thus will not be considered unexpected (please refer to the “Adverse Reaction section” in the US Package Insert (USPI) for Toujeo (9)). Any other AE not listed in the “Adverse Reaction” in the USPI will be considered as unexpected.

The Sponsor will report all safety observations made during the conduct of the trial in the clinical study report.

10.6 ADVERSE EVENTS MONITORING

All events will be managed and reported in compliance with all applicable regulations, and included in the final clinical study report.

Adverse events will be monitored until final outcome or return to patient's baseline as applicable. Follow-up information on SAEs ongoing after study completion and for which an outcome is unavailable must be reported to the Sponsor's Global Pharmacovigilance and Epidemiology department.

11 STATISTICAL CONSIDERATIONS

11.1 DETERMINATION OF SAMPLE SIZE

A sample size of 150 patients (75 in virtual approach and 75 in traditional approach) will be randomized using a 1:1 ratio (virtual:traditional); this sample size was not powered for confirmatory testing, only descriptive statistics will be provided.

As this is a pilot study, no formal sample size calculation was performed.

Nevertheless, a precision calculation of the primary endpoint based on the 2-sided 95% confidence interval (CI) shows that the change in HbA1c from baseline in virtual approach, the change in HbA1c from baseline in traditional approach and the difference in HbA1c change between the two approaches will be estimated with a precision of approximately 0.37%, using a standard deviation (SD) of 1.1 and taking into account an up to 10% rate of non-evaluable patients for HbA1c. These calculations were made using nQuery Advisor 7.0.

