	
 - Diabetes Treatment Satisfaction Questionnaire change (DTSQc), administered on Week 24 only - Hypoglycemia Fear Survey-II (HFS-II) - Diabetes Distress Scale (DDS) • HbA1c: change from baseline to Week 16 • FPG: change from baseline to Week 16 and Week 24 • Change in 7-point SMPG profiles, mean and per time-point from baseline to Week 16 and Week 24, • Insulin doses 
Patient care with the two approaches:
 
 • Study-specific resource requirements: Overall Study Experience-Sites (OSES) questionnaire part 1 (resource requirements) over the 24 week treatment period • Site-perceived patient relationship and satisfaction: OSES questionnaire part 2 at Week 24 • Patient interview in a subset of patients at Week 24 
Safety assessment managed by the two approaches:
 
 • Hypoglycemic events and incidence rate (as per the American Diabetes Association (ADA) classification) during the 24-week period in each group • Adverse events (including Injection site reactions and hypersensitivity), Serious AEs (SAEs) and Product Technical Complaints (PTCs)
ASSESSMENT SCHEDULE	See study flowchart in Section 1.2 .
STATISTICAL CONSIDERATIONS	
Sample size determination:
 
This is a pilot study, consequently no formal sample size calculation was done.
 
The sample size was not powered for confirmatory testing, only descriptive statistics will be provided.
 
Number of patients per trial approach group: randomization using a ratio 1 (virtual):1 (traditional).
 
Nevertheless, a precision calculation based on the 2-sided 95% confidence interval (CI) shows that the change in HbA1c from baseline in virtual approach, the change in HbA1c from baseline in traditional approach and the difference in HbA1c change between the two approaches will be estimated with a precision of approximately 0.37%, using a standard deviation (SD) of 1.1 and taking into account an up to 10% rate of non-evaluable patients for HbA1c.
 
General aspects of the analyses:
 
Except if defined below, the baseline value will be the last available value prior to the first injection of IMP.
 
Analysis population:
 
The primary population for all non-safety endpoints will be the Intent-To-Treat (ITT) population, which will comprise all randomized

[figure not shown]

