11.4 STATISTICAL METHODS

No multiplicity adjustment will be made on endpoints; 95% CIs presented for these endpoints will be calculated for descriptive purpose only.

Except if defined below, the baseline value will be the last available value prior to the first injection of IMP.

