1.3 DETERMINATION OF SAMPLE SIZE

A sample size of 150 patients (75 in virtual approach and 75 in traditional approach) will be randomized using a 1:1 ratio (virtual: traditional); this sample size was not powered for confirmatory testing, only descriptive statistics will be provided.

As this is a pilot study, no formal sample size calculation was performed.

[figure not shown]
Nevertheless, a precision calculation of the primary endpoint based on the 2-sided 95% confidence interval (CI) shows that the change in HbA1c from baseline in virtual approach, the change in HbA1c from baseline in traditional approach and the difference in HbA1c change between the two approaches will be estimated with a precision of approximately 0.37%, using a standard deviation (SD) of 1.1 and taking into account an up to 10% rate of non-evaluable patients for HbA1c.

These calculations were made using nQuery Advisor 7.0.

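### One 95% CI precision of 0.37% HbA1c is given for each within-approach change and for their difference; it fits only the difference, and the within-approach figure is about 0.26 to 0.27%.

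*Protocol*

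**What the plan says.** Protocol 11.1 plans 75 patients per approach and states that "As this is a pilot study, no formal sample size calculation was performed". In place of a power calculation it offers "a precision calculation of the primary endpoint based on the 2-sided 95% confidence interval (CI"). The precision is about 0.37%, and it is attached to three estimates at once: "the change in HbA1c from baseline in virtual approach, the change in HbA1c from baseline in traditional approach and the difference" in change between the approaches. The inputs are given as "using a standard deviation (SD) of 1.1 and taking into account an up to 10% rate of non-evaluable patients for HbA1c". The software is named as nQuery Advisor 7.0, but the text does not say whether normal or t quantiles were used.

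The synopsis has the same sentence ("will be estimated with a precision of approximately 0.37%, using a standard deviation (SD) of 1.1"), and so does SAP 1.3 ("will be estimated with a precision of approximately 0.37"). Neither document gives a separate figure for the change within one approach, and neither says whether 1.1 is the SD of the change or of a single HbA1c value.

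**The concern.** The variance of a difference between two independent means of equal size and equal SD is twice the variance of either mean. The confidence interval for the difference must therefore be wider than the interval for each approach by a factor close to the square root of 2. A sentence that gives all three the same precision is wrong for at least one of them.

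This is the only quantitative support offered for 150 patients, and it concerns the primary endpoint. Protocol 11.4.2.1.1 will report an adjusted mean with a 95% CI for each approach as well as for the difference, so the within-approach figure describes a planned output. Protocol section 4 presents the study as a pilot before full-scale studies, and a reader planning one of those could take 0.37% as the precision of a single arm.

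**Working it through.** **Inputs (Protocol 11.1).** Two-sided 95% CI; SD 1.1; 75 randomized per approach; up to 10% non-evaluable, so 75 × 0.90 = 67.5, that is 67 or 68 evaluable per approach. Assumption: 1.1 is the SD of the change from baseline, the natural reading because the sentence deals only with changes. An alternative is tested below.

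**Formulas.** With q the 97.5% quantile (1.960 for the normal; t on 2n − 2 df for the difference and n − 1 df for one arm):

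- difference: q × SD × √(2/n)
- one approach: q × SD / √n

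**The plan's own figure.** For the difference with normal quantiles:

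- n = 67: 1.960 × 1.1 × √(2/67) = 0.372
- n = 68: 1.960 × 1.1 × √(2/68) = 0.370

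The stated 0.37% is reproduced for the difference.

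**One approach, same inputs, normal quantiles.**

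- n = 67: 1.960 × 1.1 / √67 = 0.263
- n = 68: 1.960 × 1.1 / √68 = 0.261

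**With t quantiles alongside:**

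| Evaluable per approach | Difference, normal | Difference, t | One approach, normal | One approach, t |
|---|---|---|---|---|
| 67 | 0.372 | 0.376 | 0.263 | 0.268 |
| 68 | 0.370 | 0.373 | 0.261 | 0.266 |

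The ratio of difference to single approach is 1.414 (normal) or 1.401 (t). The stated 0.37 divided by the single-approach value is 1.40 to 1.42 (normal) or 1.38 to 1.39 (t).

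**Other reading of the SD.** Suppose 1.1 is the SD of one HbA1c value and baseline and Week 24 are uncorrelated (an assumption; the documents give no correlation). The SD of the change is then 1.1 × √2 = 1.556. One approach has a half-width of 0.370 to 0.379, but the difference has 0.523 to 0.532. The mismatch moves to the other part of the sentence.

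**What SD of change would be needed.**

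- 0.37 for the difference: 1.093 to 1.101 (normal) or 1.083 to 1.091 (t)
- 0.37 for one approach: 1.545 to 1.557 (normal) or 1.517 to 1.529 (t)

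The ranges do not overlap, so no single SD satisfies the sentence.

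**Other conventions, one approach, SD 1.1.**

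- No allowance for non-evaluable patients (n = 75): 0.249 (normal) or 0.253 (t)
- One-sided 95% limit: 0.219 to 0.221
- Full interval width: 0.523 to 0.527
- Half-width adjusted for 80% to 95% coverage probability: 0.285 to 0.306

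None gives 0.37. At SD 1.1, a half-width of 0.37 in one approach corresponds to (1.960 × 1.1 / 0.37)² ≈ 34 evaluable patients, half the planned number.

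**The case against.** The strongest reply is that the figure that matters is right. The primary objective compares virtual with traditional conduct, and 0.37% reproduces for that comparison. For the single approaches the error is on the safe side, because the real interval would be narrower than stated, and a reader might take 0.37% as an upper limit for all three. The sample size was not derived from it, Protocol 11.4 says that "95% CIs presented for these endpoints will be calculated for descriptive purpose only", and no decision depends on it. Finally, SAP section 2 reports early termination with 15 patients randomized instead of 150 and only basic descriptive statistics to follow, so neither 0.37% nor 0.26% describes the precision achieved.

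Most of this stands, and it limits the consequence. It does not rescue the sentence. The text does not say at most 0.37%; it says each of the three will be estimated with about that precision, and the word for approximately does not stretch from 0.26 to 0.37. Early termination removes the practical effect on this trial's analysis but does not make the planning statement correct.

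A further fair point is that the documents do not settle the second decimal. With t quantiles and 68 evaluable patients, the difference still rounds to 0.37 while one approach rounds to 0.27. The single-approach figure should therefore be given with its method and n, and 0.26 to 0.27% is the range the documents support.

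**Conclusion.** The concern holds. One precision cannot apply to both the within-approach changes and their difference; that conclusion needs only equal evaluable numbers and a common SD, not a particular reading of 1.1. If 1.1 is the SD of the change and 67 or 68 patients per approach are evaluable, about 0.37% is correct for the difference and wrong for each approach, where it should be about 0.26% (normal) or 0.27% (t). The stated figure is then 38% to 42% too wide for two of the three quantities.

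The severity is minor. The error is conservative on that reading, and it affects neither the sample size nor the analysis.

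**What to change.** Reword the sentence identically in the synopsis, Protocol 11.1 and SAP 1.3, for example:

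> The half-width of the 2-sided 95% CI is about 0.26% for the HbA1c change within each approach and about 0.37% for the difference between approaches (normal approximation, SD of the change 1.1, 67 to 68 evaluable patients per approach).

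If t-based values are preferred, state the n: 68 gives 0.27% and 0.37%; 67 gives 0.27% and 0.38%. If 1.1 is not the SD of the change, state the SD of the change that was used and recompute both figures.

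The cost is one sentence in three places, with no change to the sample size, model or outputs. The protocol text must follow the amendment route in Protocol section 15, which requires ethics committee approval. Since the trial has already stopped, a correcting note in the clinical study report would be a proportionate alternative if the sponsor does not wish to amend.

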11.2 DISPOSITION OF PATIENTS

Screened patients are defined as any patient who met the inclusion criteria and signed the informed consent.

Randomized patients consist of all screened patients with a trial approach group allocated and recorded in the IRT database, regardless of whether the treatment kit was used or not.

For any patient randomized more than once, only the data associated with the first randomization will be used in any analysis population. The safety experience associated with any later randomization will be assessed separately.

The safety experience of patients treated and not randomized will be reported separately, and these patients will not be in the safety population.

The total number of patients for each of the following categories will be presented.

- Screened patients
- Screen failure patients and reason for screen failure
- Randomized patients
- Safety population ([Section 11.3.2](#)) presented as treated
- The intent-to-treat (ITT) population ([Section 11.3.1](#)) analyzed as randomized
- The randomization strata (sites and screening HbA1c categories [$<7.6\%$, $\geq 7.6\%$] assigned by IRT); the discrepancy between the strata assigned by IRT and the information reported on e-CRF will be listed for all randomized patients

- Patients who permanently discontinued the IMP, and the reasons for permanent treatment discontinuation
- Patients who completed the 24-week treatment period (patients who have attended Visit 12, who did not permanently discontinue treatment, and who did not take any rescue medication)
- Patients who did not complete the 24-week treatment period
- Patients who discontinued 24-week treatment by main reason for permanent treatment discontinuation
- Patients who completed the study (patients who have attended Visit 12, whichever the treatment duration)
- Patients who did not complete the study (patients who have not attended Visit 12)
- Patients who discontinued the study by main reason for study discontinuation

For all categories of patients except screened and screen failure patients, percentages will be calculated using the number of randomized patients as denominator for each approach group.

Patients with the following deviations will be identified and described in separate listings:

- Treated but not randomized
- Randomized but not treated
- Randomized but not treated as randomized

A list of patients prematurely discontinued from the treatment, along with reasons for discontinuation, will be provided.

11.3 ANALYSIS POPULATIONS

11.3.1 Intent-to-treat population

The ITT population will be used to analyze all non-safety endpoints. It consists of all randomized patients, irrespective of the trial approach group actually being used, analyzed according to the approach group allocated by randomization.

11.3.2 Safety population

The safety population is defined as all randomized patients who did actually receive at least one dose of IMP, regardless of the amount of IMP administered.

In the event of patients having followed a trial approach that differed from the one assigned according to the randomization schedule, the safety analyses will be conducted according to the trial approach group assigned by randomization.

Patients will not be considered exposed if there is documented evidence that patients have not taken the study drug:

- If a patient is dispensed IMP and is lost to follow-up without any documented evidence, the patient will be considered exposed and included in the safety population
- Randomized patients for whom it is unclear whether they took the study medication will be included in the safety population as randomized

In addition:

- Non randomized but treated patients will not be part of the safety population, but their safety data will be presented separately

11.3.3 PRO population

The analysis of PROs will be conducted on the ITT population.

11.4 STATISTICAL METHODS

No multiplicity adjustment will be made on endpoints; 95% CIs presented for these endpoints will be calculated for descriptive purpose only.

Except if defined below, the baseline value will be the last available value prior to the first injection of IMP.

11.4.1 Extent of study treatment exposure and compliance

The extent of study treatment exposure and compliance will be assessed and summarized by randomized trial approach group within the safety population.

11.4.1.1 Extent of investigational medicinal product exposure

The duration of exposure during the study will be the total number of days of administration of IMP, regardless of unplanned intermittent discontinuations.

The duration of exposure to the open-label IMP during the study is defined as:

(Date of the last IMP administration – date of the first IMP administration) + 1 day.

Duration of IMP exposure will be summarized descriptively as a quantitative variable (number, mean, SD, median, minimum, and maximum). In addition, duration of treatment exposure will also be summarized categorically by numbers and percentages for each of the following categories and cumulatively according to these categories:

- up to 4 weeks
- >4 to 8 weeks
- >8 to 12 weeks
- >12 to 16 weeks
- >16 to 20 weeks

- >20 to 22 weeks
- >22 to 23 weeks
- >23 to 24 weeks
- >24 weeks

11.4.1.2 Compliance

A given administration will be considered noncompliant if the patient did not take the planned dose of treatment as required by the protocol. No imputation will be made for patients with missing or incomplete data.

Treatment compliance percentage will be summarized descriptively (N, Mean, SD, Median, Min, and Max). The percentage of patients with compliance is <80% will be summarized.

11.4.2 Analysis of primary endpoint

Primary endpoint is described in [Section 9.1](#).

11.4.2.1 Analysis of primary efficacy endpoint

11.4.2.1.1 Primary analysis

The change in HbA1c from baseline to Week 24 will be analyzed using available data during the 24-week randomized period. A mixed effect model with repeated measures (MMRM) approach will be used, under the missing at random framework carried out via SAS PROC MIXED using an adequate contrast at Visit 12 (Week 24).

This model will be run with an unstructured correlation matrix to model the within-patient errors. Parameters will be estimated using restricted maximum likelihood method with the Newton Raphson algorithm. Denominator degrees of freedom will be estimated using Satterthwaite's approximation. This model will provide baseline adjusted least squares means estimates at Week 24 for both approach groups, as well as the differences of these estimates, with their corresponding standard errors and 95% CIs.

The model will include fixed categorical effects of trial approach group, visit, trial approach-by-visit interaction, randomization stratum of sites; and the continuous fixed covariates of baseline HbA1c value and baseline HbA1c value-by-visit interaction.

